# 2.4.3 Primary Effectiveness Analysis

Responder rate for each treatment based on the GJS, as assessed live by the Blinded Evaluator at 3 months after last treatment for the Treatment group and after baseline for the No Treatment group, will be the primary effectiveness endpoint. A responder will be defined as a subject with at least 1 grade improvement from baseline, on both jawlines concurrently.

The null hypothesis will be that there is no relationship between responder rate and treatment group (i.e., the responder rate is the same in treated and untreated subjects). The alternative hypothesis will be that there is a relationship between responder rate and treatment group (i.e., the responder rate is different in treated subjects compared to untreated subjects).

The estimates of the responder rate in each group will be presented as well as the difference in responder rates. Corresponding confidence intervals for responder rates (via Clopper-Pearson) and the difference in responder rates (via normal approximation) along with the p-value (via Fisher's exact test) for the difference will also be presented. For a significant result, the two-tailed p-value of the comparison of responder rates between the treated and untreated subjects at 3 months using the Fisher's exact test needs to be smaller than 0.05.

A forest plot of the treatment difference in Month 3 responder rates for the GJS will be provided.

[figure not shown]
# 2.4.4 Secondary Effectiveness Analysis

(i) To assess the effectiveness of *Restylane Lyft Lidocaine* for Jawline definition, the following will be presented:

The responder rate on the GJS as assessed live by the Blinded Evaluator at 6, 9 and 12 months after last treatment for the Treatment group and after baseline for the No Treatment group will be presented as well as the difference in responder rates between groups. Corresponding confidence intervals for responder rates and the difference in responder rates will also be presented. A bar plot of the percentage of responders by visit will be produced for Blinded Evaluator and presented by treatment group.

The responder rates based on the GAIS as assessed by the investigator and the subject, respectively, at each visit will be calculated and presented along with their 95% confidence intervals for each treatment group. The difference in responder rate between the two groups will be presented along with a 95% confidence interval.

In addition, the GJS and GAIS (for subject and investigator) will be presented with number of subjects and percentage for each category of the scales for each visit by treatment group.

#### 2.4.5 Subgroup Analyses

Supgroup analyses will be performed on age groups: less than or equal to median age, greater than median age. The statistical testing performed on the primary and secondary efficacy analyses will be repeated by age group.

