Total Number of Subjects (Planned):	Approximately 140 subjects will be randomized (3:1) to Treatment or to No Treatment group.		
Effectiveness Objectives and	The primary objective of the study is to assess the effectiveness of		
Endpoints:	Restylane Lyft Lidocaine versus a no treatment control in jawline definition by comparing Colderma Jawline Scale (CJS) response rates		
	Primary Endpoint		
	Responder rate based on the Blinded Evaluators' live assessment of the		
	GJS at 3 months after last treatment for the Treatment group or after baseline for the No Treatment group.		
	A responder is defined as a subject with at least 1-point improvement from baseline, on both jawlines concurrently.		

MA-52559

	The secondary objective is to assess the effectiveness of Restylane Lyft Lideoging for inviling definition
	Luocaine for Jawine definition.
	1. Responder rates based on the Blinded Evaluator's live assessment using the GJS at 6, 9 and 12 months after last treatment for the Treatment group or after baseline for the No Treatment group. A responder is defined as a subject with at least 1-point improvement from baseline, on both jawlines
	 Proportion of subjects having at least "Improved" on the Global Aesthetic Improvement Scale (GAIS) on both jawlines concurrently, as assessed live by the Subject and Treating Investigator separately at 3, 6, 9 and 12 months after last treatment for the Treatment group and after baseline for the No Treatment group.
	One month is defined as 4 weeks in the study.
Safety Objectives and Endpoints:	To evaluate the safety of Restylane Lyft Lidocaine by assessments of adverse events (AEs) by the Treating Investigator throughout the study period.
	 Incidence, intensity, duration and onset of AEs collected during the study period. Pre-defined, expected, post-treatment events reported for 28 days from treatment as recorded in the subject diary.
Subgroup Analyses:	Not applicable.
Clinical Study Duration:	 First subject first visit (FSFV) to last subject last visit (LSLV): Approximately 18 months including 4 months recruitment period. Treatment group:
	• Up to 21 days screening

Print date: 2022-10-27 21:48

GALDERMA EST, 1981	05DF2209, Clinical Stu
-----------------------	------------------------

Doc id

	o T	reatment at baseline (Day 1) and TC at 72 hrs after initial
		Ontional touch-up at 1 month and TC at 72 hrs after touch-up
	0 D	Data collection and safety follow-up visits at 1, 3, 6, 9 and 12

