# 2.7 Determination of Sample Size

#### 2.7.1 Sample Size

A total sample size of approximately 140 subjects will be included in this study. For the responder rate in GJS, a Fisher's exact test using a 5% two-sided significance level will have approximately 90% power to demonstrate difference between a responder rate of 70% in the *Restylane Lyft Lidocaine* group, and a responder rate of 35% in the no treatment control group when the sample sizes are 105 and 35, respectively. Accounting for 10% dropouts, approximately 140 subjects need to be randomized in a 3:1 ratio.

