# 2.8 Changes in the Analysis Planned in the Protocol

The definition of the Safety Population was updated to include subjects who were randomized to the No Treatment group.

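### SAP 2.4.5 tests each age half separately but plans no estimate of how the effect differs between them; under a uniform effect, exactly one half is significant about 41% of the time

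*SAP*

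**What the plan says.** The protocol synopsis has a row headed "Subgroup Analyses" and marks it as not applicable. Protocol section 9 plans no subgroups.

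SAP 2.4.5 introduces them. The two groups are "less than or equal to median age, greater than median age", and the method is: "The statistical testing performed on the primary and secondary efficacy analyses will be repeated by age group".

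For the primary endpoint, SAP 2.4.3 defines one test, a two-tailed Fisher's exact test that must fall below 0.05. It also presents the rate in each arm, the difference and confidence intervals. For the secondary endpoints, SAP 2.4.4 gives rates, differences and confidence intervals but names no test.

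Neither document contains a treatment-by-age contrast or a rule for reading the two age halves together. SAP 2.8, the section for changes from the protocol, has one entry: "The definition of the Safety Population was updated to include subjects who were randomized to the No Treatment group". The age subgroups are not listed there.

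**The concern.** An age subgroup is there to ask whether the product works differently in younger and older subjects. The answer is the difference between the two effects. Two separate p-values do not give it, because one can fall below 0.05 and the other above when the effects are the same.

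This trial is prone to that pattern. The control arm has 35 subjects, so a median split leaves 17 or 18 controls in each half, and power per half is far below that of the whole trial. A report with one significant and one non-significant age group, and nothing comparing them, invites the reader to conclude that the product works in one group only. At stake is the interpretation of the subgroup table. The trial's main result is not at stake.

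**Working it through.** **Inputs.** All are from SAP 2.7.1 unless noted.
- Test: "a Fisher's exact test using a 5% two-sided significance level will have approximately 90% power".
- Treatment arm: "a responder rate of 70% in the" active group.
- Control arm: "a responder rate of 35% in the no treatment control group when the sample sizes are 105 and 35, respectively".
- Dropout and allocation: "Accounting for 10% dropouts, approximately 140 subjects need to be randomized in a 3:1 ratio".
- Missing primary data are handled by BOCF (SAP 2.4.2), so a missing subject counts as a non-responder.
- Assumption: the arms split evenly at the median, 53/18 and 52/17. The documents do not give this. Randomization is not described as stratified by age, and ties at the median go to the lower group.

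**Method.** Exact power is the sum, over all responder counts x (treatment) and y (control), of Bin(x; nT, pT) × Bin(y; nC, pC), kept where the two-sided Fisher p is below 0.05.

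**The plan's own figure.** At 105/35 and 70% vs 35%, exact power is 95.0%. Taking 10% dropout off 140 leaves 126, and power is then 91.7% at 95/31 and 93.0% at 94/32. The stated figure of about 90% therefore reproduces if 105 and 35 are the numbers before dropout.

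**Power in each half, same 70% vs 35% in both.**
- 53/18: 71.5%
- 52/17: 70.9%

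**Joint probabilities** (the halves contain different subjects and are treated as independent).
- Exactly one half significant: 0.715 × (1 − 0.709) + 0.709 × (1 − 0.715) = 0.208 + 0.202 = 41.0%
- Neither significant: 0.285 × 0.291 = 8.3%
- At least one non-significant: 41.0% + 8.3% = 49.3%

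**With BOCF dilution.** If 10% of each arm become non-responders regardless of outcome, the rates are 0.9 × 70% = 63% and 0.9 × 35% = 31.5%. Power is 58.1% and 59.1%. Exactly one half significant: 0.581 × 0.409 + 0.591 × 0.419 = 48.5%.

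**Range over the assumptions.**

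| Scenario | Sizes by half | Exactly one significant | At least one non-significant |
|---|---|---|---|
| Even split, no dropout | 53/18, 52/17 | 41.0% | 49.3% |
| Other rounding | 53/17, 52/18 | 41.9% | 50.8% |
| Arms fall at random across the median (simulation) | varies | 43.1% | 52.3% |
| 126 evaluable | 47/16, 47/16 | 44.8% | 56.3% |
| 125 evaluable | 47/16, 47/15 | 46.4% | 59.5% |
| 10% BOCF dilution | 53/18, 52/17 | 48.5% | 65.6% |

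**Precision of the missing contrast.** The variance of the difference between the two risk differences is the sum of four binomial variances:

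0.7 × 0.3/53 + 0.35 × 0.65/18 + 0.7 × 0.3/52 + 0.35 × 0.65/17 = 0.0040 + 0.0126 + 0.0040 + 0.0134 = 0.0340

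The SE is √0.0340 = 0.184, and the 95% half-width is 1.96 × 0.184 = 0.36, or about 36 points.

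**Check on direction.** Under the same assumptions as the first row, the chance that the observed difference is zero or negative in at least one half is 0.9%.

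**The case against.** Five points can be made for the plan.

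- **Success rests on one overall test.** The synopsis ties formal testing to the primary objective, and Protocol 9.4 treats p-values for endpoints other than the primary as interpretive. This stands: neither document says an age effect will be concluded from the halves, so the misreading is a risk and not a planned inference. However, the wording in Protocol 9.4 does not name a subgroup test of the primary endpoint itself, and SAP 2.4.5 does not call the analysis exploratory.
- **Half-specific differences and intervals are arguably already planned.** SAP 2.4.3 presents them with the p-value. SAP 2.4.4 has no test to repeat, so the sentence in 2.4.5 makes sense for the secondary endpoints only if differences and intervals are what is repeated. This is a fair reading, and it reduces the change needed. It still leaves out the contrast between the halves.
- **The SAP may depart from the protocol.** SAP 2.1 says so and gives the SAP precedence. Adding the subgroup is therefore allowed, and its absence from 2.8 is a documentation gap.
- **The contrast would be imprecise.** At about ±36 points it cannot separate a uniform effect from a sizeable age difference. That is true, and showing it is useful, because two p-values conceal how little the data say about age.
- **The size depends on an assumed split.** That is also true. The tabulated alternatives run from 41% to 49% for exactly one significant half.

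A reader might also infer that a uniform effect has about an even chance of seeming absent in one age group. The figures do not support this. The 49.3% is the chance of p ≥ 0.05 in at least one half, and non-significance is not absence of effect. It also includes the 8.3% in which neither half is significant, a pattern that would not suggest an age difference.

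**Conclusion.** The point holds as a gap in the subgroup method. SAP 2.4.5 repeats the primary test in each age half and omits the one quantity that addresses variation with age. With the same 70% vs 35% effect in both halves, there is about a 41% chance that exactly one half reaches p < 0.05, rising to about 49% with 10% BOCF dilution. This rests on an even split of the arms at the median and on independent halves. The BOCF figure also assumes equal dropout in both arms, unrelated to response.

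A reader might infer that the repeated tests inflate the trial's type I error or weaken its main conclusion. The documents do not support that: success is decided by the overall Fisher test alone, and the subgroup results do not feed into it.

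**What to change.** In SAP 2.4.5:
- State that the responder-rate difference with its 95% CI will be reported in each age half. For the secondary endpoints, say explicitly that this is what is repeated.
- For the primary endpoint, add the difference between the two risk differences with its 95% CI. This is simple subtraction, with the SE taken as the root of the four summed variances, and needs no model.
- Drop the within-half p-values, or state that they are not evidence of an age effect.
- Label the analysis exploratory.

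In SAP 2.8, list the age subgroups as an addition to the protocol.

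The cost is a few sentences and one derived line in a table. It needs no new data or subjects and leaves the primary analysis as it is. Under SAP 2.1, a change to the finalized SAP before database lock is made as an SAP amendment.

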#### 2.5 Safety Analysis

Safety endpoints will be summarized using descriptive statistics by treatment group based on the Safety population using observed cases. There are no planned inferential statistical analyses of safety endpoints.

Subjects in the No Treatment group who elect for an optional treatment will also be included in the Treatment Administration and Adverse Events summaries.

#### 2.5.1 Treatment Administration, Post-injection Care, and Procedural Anesthetics

Injection volume, injection method(s), depth of injection and needle and cannula size will be summarized for each treatment session by treatment area for each treatment group.

Injection volume overall, number of syringes, needles and cannulas will be summarized by treatment session for each treatment group.

The number of subjects with any procedural anesthetics and post-injection procedures will be summarized by type.

#### 2.5.2 Adverse Events (AEs)

AEs will be summarized relative to the treatment session timing using the following categories:

- No Treatment at Baseline: Subjects who receive no treatment at baseline, include AEs before any optional *Restylane Lyft Lidocaine* treatment at Month 12.
- Initial Treatment with *Restylane Lyft Lidocaine*: Subjects who were initially treated with *Restylane Lyft Lidocaine* at Baseline.
- Optional Treatment at 12 Month Visit: Subjects who received no treatment at baseline and were treated with *Restylane Lyft Lidocaine* at the 12 month visit. Includes AEs that occur after optional treatment.

• Total *Restylane Lyft Lidocaine*: Includes all subjects who were initially treated with *Restylane Lyft Lidocaine* at baseline or treated at the optional 12 month visit.

All AEs will be coded according to MedDRA and summarized by System Organ Class (SOC), Preferred Term (PT), and treatment. The number of subjects with at least one event, associated percentage, and number of events will be provided.

For subject counts, a subject will only be counted once per SOC and once per PT in cases where multiple events are reported for a subject within SOC or PT. For event counts, subjects with multiple events in a category will be counted for each event.

The number of subjects with AEs related to study product or study product injection procedure and unrelated AEs will be presented by SOC, PT, and maximum intensity. Action taken for related AEs will also be summarized by SOC and PT using number of events.

Serious AEs (SAEs) will be listed.

For AEs related to study product or study product injection procedure, the number of days to onset and the duration of event will be summarized by SOC and PT using mean, standard deviation, median, minimum, and maximum. Days to onset of an AE will be derived as the start date minus the date of most recent treatment session. Duration of an AE will be derived as the stop date minus the start date + 1.

For the purpose of deriving days to onset and duration, the following date imputation rules will be used.

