Safety Assessments	 Adverse Event reporting: AEs will be obtained from signs and symptoms reported by the subject or detected during each examination. A subject diary will be dispensed to the Treatment group for daily completion over the first 28 days after each treatment to record the following pre-identified symptoms: bruising, redness, pain, tenderness, lumps/bumps, itching, swelling and other. Information from the diary will be presented separately from other AEs. Device deficiencies will be assessed at treatment visits 	

MA-52559

Doc id

CLINICAL STUDY FLOW CHART

Figure 1 Study Flow Chart

Title

All subjects should complete the visits stated in the flow-chart below. Subject receiving treatment should also complete Safety follow-up visits by Phone and additional follow-up visits as indicated. Subjects in the No Treatment group will be offered an optional treatment after 12 months from baseline (Day 1) followed by a safety assessment 2 weeks after the optional treatment.

¹If no optional treatment, the visit will be the EOS visit: EOS = End of study; FUP = Follow-up; hrs = hours; TC = Telephone call; Tx = Treatment; TU = Touch-up

col R Lyft Jawline CA	
MA-52559	
D	MA-52559

SCHEDULE OF EVENTS

Table 1Schedule of events – Treatment group

Procedure	Visit 1	Visit 2	Visit 2a	Visit 3	Visit 3a ⁴	Visit 3b ⁴	Visit 4	Visit 5-6	Visit 7
	Day -21 to 1	Day 1	72 hrs after Tx (±24 hrs)	1 month after Tx (+7 days)	72 hrs after optional TU (±24 hrs)	1 month after optional TU (+7 days)	3 months after last treatment (±14 days)	6 and 9 months after last treatment (±14 days)	12 months after last treatment (±14 days)
	Screening	Baseline/ Tx	ТС	Follow-up/ Optional TU	TC	Follow-up	Follow-up	Follow-up	Follow-up/ EOS
nformed Consent	Х								
Med. Hx/prior therapies	Х	X ^{1,2}							
Demographics	Х								
Height/Weight ⁹		X^1							Х
nclusion/Exclusion Criteria	Х	X ^{1,2}		X ^{1,5}					
Urine pregnancy test ³	Х	X ^{1,2}		X ^{1,5}					
Randomization		X^1							
Freatment with study product		Х		X ⁵					
Evaluate device deficiencies		Х		X ⁵					
Dispense Subject Diary		Х		X ⁵					
Collect/Review Subject Diary			X ⁸	Х	X ⁸	Х			
Photography		X^1		X ¹		Х	Х	Х	Х
Concomitant therapies	Х	X ²	Х	Х	Х	Х	Х	Х	Х
Assessment of AEs		Х	Х	Х	Х	Х	Х	Х	Х
Freating Investigator Assessments					•				
GAIS							X	Х	X
Galderma Jawline Scale ⁶	Х	X ^{1,2}		X ^{1,5}					
Blinded Evaluator Assessments									
Galderma Jawline Scale	Х	X ^{1,2}					Х	Х	Х
Subject Assessments									
GAIS							Х	Х	Х

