7.2 Subject Diary Data

The Subject from the Treatment group shall evaluate local tolerability in a 28 days diary, starting on the day of each treatment. The presence and maximum intensity of pre-defined, expected post-treatment events, i.e., bruising, redness, pain, tenderness, lumps/bumps, itching and swelling shall be assessed for the treated area.

The Investigator or study staff should review the diary for completion and clarify any events as needed. For events that are ongoing at the time of diary completion, the Investigator should follow them and record resolution in the subject's study file and eCRF. Diary data will be analyzed and displayed separately from AE data.

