7.7 Safety report procedures and timelines

Safety evaluations for this study include an interview of the subjects at each visit to obtain information about any medical occurrence that meets the definition of an AE. Each subject should be questioned about AEs at each study visit following the baseline visit. An event that occurs after the subject signs the ICF but before enrollment (i.e., randomized and/or treated) will be recorded in the subject's medical history. The question about AEs should be asked: "Since your last clinical visit have you had any health problems?" Information on AEs can also be obtained from signs and symptoms detected during each examination by the Investigator or designee, which should include visual inspection of the treatment area or from a laboratory test, subject diaries, or spontaneous reports from the subjects or their relatives.

AEs must be documented in the source document and eCRF without regard for cause or relation to investigational product. If in the process of the interview, additional information regarding medical history or pre-planned medical or surgical procedures is revealed, it must be documented in the source document(s) and eCRF.

It is the responsibility of the Investigator to determine severity of the AE and relatedness of the event to the study product.

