8.2 Visit 2: Baseline (Day 1, Initial Treatment)

The screening visit and baseline visit (Day 1) may be performed on the same day if a subject is deemed eligible by the Treating Investigator.

If screening visit and baseline/Day 1 visit are not performed on the same day, the following procedures should be repeated at the baseline/Day 1 visit:

- Review for changes in medical history and concomitant therapies.
- Re-confirm eligibility criteria.
- Perform UPT for all females of childbearing potential Test result must be negative for the subject to be eligible for study treatment.
- Assess GJS Treating Investigator and Blinded Evaluator (see Section 6.3).

Once the subject is deemed eligible for study participation by the Treating Investigator, the following procedures should be completed:

- Record the subject's self-reported height and weight.
- Obtain pre-treatment photographs of the jawline.
- Randomize the subject to treatment or to no treatment.
- Obtain pre-treatment/baseline responses to the CCI with Lower Face and Jawline.

For subjects randomized to no treatment:

• Schedule Visit 3, 1 month (+7 days) after baseline visit),

For subjects randomized to treatment:

- Subjects will be injected with the study product.
- Record all concomitant medications/procedures used prior, during, or after the injection session.
- Record the number of syringes used and the volume of study product injected per treatment area during the injection session. Record the injection details (i.e., injection method and depth of injection).
- Evaluate for device deficiencies. If deficiencies are noted, complete form as specified in section 7.7.3.
- Evaluate post-injection AEs by Treating Investigator.
- Dispense Subject Diary and instruct subject on Diary completion. Remind the subject to bring the diary to next on-site study visit.
- Schedule the 72 hours (±24 hours) follow-up phone call (Visit 2a).
- Schedule Visit 3, 1 month (+7 days) after the baseline visit (Visit 2).

8.2.1 Visit 2a: Follow up 72-hour (±24 hours) telephone call after initial treatment

Visit conducted for subjects randomized to treatment only.

- Interview subject regarding any concomitant therapies.
- Interview subject regarding any AEs that have occurred since receiving treatment. If AEs are reported, notify the Investigator immediately and determine whether subject should return to the site for an unscheduled visit. The Investigator should assess all reported AEs in a timely manner.

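### The SAP's side-by-side AE tables compare arms with unequal follow-up and unequal AE questioning, so the all-AE and unrelated-AE rows can lean modestly against the product

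*SAP*

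**What the plan says.** SAP 2.8 records one change from the protocol: "The definition of the Safety Population was updated to include subjects who were randomized to the No Treatment group". It gives no reason. SAP 2.5 then states: "Safety endpoints will be summarized using descriptive statistics by treatment group based on the Safety population using observed cases", and adds that no inferential safety analysis is planned.

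SAP 2.5.2 defines the table columns. The untreated column is "Subjects who receive no treatment at baseline, include AEs before any optional" treatment at Month 12. The next column covers subjects treated at baseline, over their whole follow-up. Each gets numbers of subjects, percentages and numbers of events, for all AEs and separately for related and unrelated AEs. There is no common time window, no adjustment for exposure and no note on how AEs were found.

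The schedule differs by arm:

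- Diary. Protocol 7.2: "The Subject from the Treatment group shall evaluate local tolerability in a 28 days diary, starting on the day of each treatment". The synopsis says the same. Table 2 of the protocol gives controls no diary.
- Telephone call at 72 hours. Protocol 8.2.1: "Visit conducted for subjects randomized to treatment only". Its content includes: "Interview subject regarding any AEs that have occurred since receiving treatment".
- After a touch-up, a second call (Visit 3a) and an extra visit (Visit 3b), both with AE questioning (Protocol 8.3.1 and 8.3.2).
- Clock. Treated subjects are followed for 12 months from last treatment, controls for 12 months from baseline (Protocol 3.4).

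Protocol 7.7 says AE information may come from examination "or from a laboratory test, subject diaries, or spontaneous reports from the subjects or their relatives". Protocol 7.2 says diary data are displayed apart from AE data.

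**The concern.** Once the untreated column stands beside the treated one, readers will compare them, above all in the all-AE and unrelated-AE rows. Two features of the design can separate those rows when the true background rates are equal. A touched-up subject has more days on which an AE can start and be counted. Treated subjects are also asked sooner and more often, and a daily record may prompt events that a control would have forgotten by the next visit. Neither feature is visible in a table of crude percentages. What is at stake is how the descriptive safety table is read; the primary endpoint and the related-AE results are not touched.

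**Working it through.** The documents give no figure for this comparison, so there is none to reproduce. The check has two parts.

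**Scheduled AE contacts after baseline** (Protocol Tables 1 and 2, section 8)

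| | Control | Treated, no touch-up | Treated, touch-up |
|---|---|---|---|
| Contacts in total | 5 | 6 | 8 |
| Contacts by week 8 | 1 | 2 | 4 |
| First contact | day 28 | day 3 | day 3 |
| Diary days | 0 | 28 | 56 |
| Follow-up | 48 weeks | 48 weeks | 52 weeks |

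One month is 4 weeks (Protocol 2.1.2), so 12 months is 336 days. Visit 3 may be up to 7 days late, so a touch-up adds 28 to 35 days.

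**Illustrative event ratio under equal true rates.** Assumptions, none of them in the documents: background AEs arise at a constant rate; a share p of treated subjects is touched up, at day 28; every AE starting on a diary day is captured; on all other days, in both arms, a fraction c is captured.

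- Mean treated follow-up = 336 + 28p.
- Diary days = 28 + 28p, so non-diary days = 308 whatever p is.
- Ratio from follow-up alone = (336 + 28p)/336.
- Total recorded ratio = (308c + 28 + 28p)/(336c).
- Part due to questioning = total divided by the follow-up ratio.

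| p | Follow-up alone | Total, c = 0.8 | Questioning part | Total, c = 0.5 | Questioning part |
|---|---|---|---|---|---|
| 0 | 336/336 = 1.00 | 274.4/268.8 = 1.02 | 1.02 | 182/168 = 1.08 | 1.08 |
| 0.5 | 350/336 = 1.042 | 288.4/268.8 = 1.073 | 1.03 | 196/168 = 1.167 | 1.12 |
| 1 | 364/336 = 1.083 | 302.4/268.8 = 1.125 | 1.04 | 210/168 = 1.25 | 1.15 |

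With the touch-up at day 35 and p = 0.5, mean follow-up is 336 + 17.5 = 353.5 days. The follow-up ratio is 353.5/336 = 1.05. The total at c = 0.8 is (0.8 × 311.5 + 42)/268.8 = 291.2/268.8 = 1.08, and the questioning part is still 1.03.

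These ratios concern event counts, not percentages of subjects.

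**Days used in the fix.** The latest in-window Visit 3b is Day 1 + 35 + 35 = 71. Forty-eight weeks after Day 1 is Day 337. The earliest in-window control Visit 7 is Day 337 − 14 = 323.

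**The case against.** The strongest reply is that no between-group AE difference is planned. The safety objective is to describe AEs with the product, and any subtraction is the reader's own. That stands, and it limits the point to how the tables are read.

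Other replies also carry weight:

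- Protocol 7.2 and SAP 1.4 confine the diary to seven local symptoms in the treated area; only the synopsis adds a category for anything else. A jawline symptom entered as an AE would probably be judged related. The illustration lets the diary improve capture of every background AE, so it is generous to the concern.
- Visit 3 is common to both arms, and the AE question in Protocol 7.7 reaches back to the previous visit. Early control events are therefore subject to recall loss; they do not fall in unobserved time.
- Related and unrelated AEs are separated, and all AEs are listed.

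Three stronger readings are tempting, and the documents do not support them. A reader might infer that controls were added to supply a background AE rate; SAP 2.8 states no purpose. A reader might take the share of treated follow-up that falls on a diary day or beyond the control window as the bias. That share runs from 28/336 = 8.3% with no touch-up to 84/364 = 23.1% if all are touched up, but it is a share of time, not an error in the AE rate. A reader might also put the whole lean down to harder questioning; at p = 0.5 and c = 0.8, longer follow-up contributes more (1.042 against 1.03).

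What the replies leave in place is the difference in follow-up length, the treated-only telephone interviews and extra visit, and the diary as a named AE source, with no allowance for any of them in the tables.

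**Conclusion.** The point holds as a modest weakness of presentation. With equal true background rates, the all-AE and unrelated-AE rows can show somewhat more events in the Treatment group. At an assumed 50% touch-up, longer follow-up gives about 1.04, and questioning adds about 1.03 if interview-only capture is 80% of diary capture, or 1.07 together. Over the assumed ranges shown, the total runs from 1.02 to 1.25. The upper end needs every treated subject touched up and interviews missing half of what a diary finds.

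The direction is clearer than the size, because neither the touch-up share nor the capture fraction is in the documents. The bias runs against the product, related-AE rates in treated subjects are unaffected, and no test or formal estimate depends on it. The documents do not support a claim that the safety conclusions would be wrong.

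**What to change.** Keep every AE table planned in SAP 2.5.2 and add one descriptive table of all AEs and unrelated AEs for the untreated-at-baseline and initially treated groups:

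- Split by onset day counted from randomization in both arms: Day 1–71, Day 72–337 and after Day 337. All extra diaries, calls and visits are over by Day 71 if visits are in window.
- Give subjects at risk and events per person-time in each period.
- End each control's time at Visit 7 or optional treatment, whichever comes first, since some controls may leave from about Day 323.
- Where a partial or missing start date does not determine the period, show the AE in a separate row. Do not use the start-date imputation in SAP 2.5.2 here: it sends a wholly missing date to baseline and a missing month to the randomization month, which would load the early period.
- Footnote that treated subjects were also questioned by diary and telephone up to Day 71, that Day 72–337 is the more comparable window but not an identical one (touched-up subjects' visits run about 4 weeks later), and that AE assessors were unblinded.

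The cost is one more table from dates already collected, with no new visit, call or diary. SAP 2.1 allows supportive analyses without an amendment, but fixing the windows in advance avoids choosing them after seeing the data. The drawback is that the comparable window holds fewer events and omits the first 71 days, which the planned tables still cover.
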